13 DATA HANDLING AND RECORD KEEPING

13.1 Case Report Forms/Source Data Handling

All required study data must be entered in the eCRF created for the study. This data collection tool is a validated electronic data capture (EDC) system that contains a system generated audit trail. Data required according to this protocol are recorded by investigational site personnel via data entry into the internet-based EDC software system. The Investigator shall ensure that all data from participant visits are promptly entered into the eCRFs in accordance with the specific instructions given. The Investigator must sign each eCRF to verify the integrity of the data recorded. All internal Medpace and external investigational site personnel seeking access to the eCRF are supported by a Service Desk (if applicable). At the end of the study all data captured electronically will be provided to the Investigator on CD-ROM for archiving at the investigational site.

A list of the normal ranges for all laboratory tests to be undertaken forms part of the documentation to be collated prior to study start. If a central laboratory has been selected to conduct any or all tests, it is essential that all samples be analysed at that laboratory.

The Investigator must maintain source documents, such as laboratory reports, X-rays, ECGs, consultation reports, and complete medical history and physical examination reports. All information in the eCRF must be traceable to the source documents in the participant's file.

The Investigator/institution shall provide direct access to source data/documents for study-related monitoring, audits, IEC/IRB review and regulatory inspection.

The Sponsor or designee is responsible for the data management of this study including quality checking of the data.

13.2 Data Protection

Participants will be assigned a unique identifier by clinical research organization. Any participant records or datasets that are transferred to the Sponsor will contain the identifier only; participant names or any information which would make the participant identifiable will not be transferred. The participant must be informed that their personal study-related data will be used by the Sponsor in accordance with local data protection law. The level of disclosure must also be explained to the

participant. The participant must be informed that their medical records may be examined by Clinical Quality Assurance auditors or other authorized personnel appointed by the Sponsor, by appropriate IEC/IRB members, and by inspectors from regulatory authorities.

13.3 Dissemination of Clinical Study Data

The study will be registered and post-study results will be posted in accordance with the applicable laws and regulations. The results of this study may be published or presented at conferences/in journals.

13.4 Retention of Essential Documents

The Investigator/institution should maintain the study documents as specified in the ICH guidelines on GCP and as required by the applicable regulatory requirements. The Investigator/institution should take measures to prevent accidental or premature destruction of these documents.

Essential documents should be retained until at least 2 years after the last approval of a marketing application in an ICH region and until there are no pending or contemplated marketing applications in an ICH region or until at least 2 years have elapsed since the formal discontinuation of clinical development of the IP. These documents should be retained for a longer period, however, if required by the applicable regulatory requirements or by an agreement with the Sponsor. It is the responsibility of the Sponsor to inform the Investigator/institution as to when these documents no longer need to be retained.

14 PUBLICATION POLICY

The Sponsor shall retain the ownership of all data. When the study is complete Medpace shall arrange the analysis and tabulation of data. A clinical study report shall then be prepared, which may be used for publication, presentation at scientific meetings or submission to regulatory authorities. The Sponsor will generally support publication of multi-center studies only in their entirety and not as individual site data. In this case, a coordinating Investigator will be designated by mutual agreement. Authorship will be determined by mutual agreement and in line with the International Committee of Medical Journal Editors authorship agreements. All proposed publications based on this study must be participant to the Sponsor's approval requirements.

The Sponsor assures that the key design elements of this protocol will be posted in a publicly accessible database such as clinicaltrials.gov. In addition, upon study completion and finalization of the study report, the results of this study will be submitted for publication and/or posted in a publicly accessible database of clinical trial results.

15 CONFLICT OF INTEREST POLICY

The independence of this study from any actual or perceived influence, such as by the pharmaceutical industry, is critical. Therefore, any actual conflict of interest of persons who have a role in the design, conduct, analysis, publication, or any aspect of this study will be disclosed and managed. Furthermore, persons who have a perceived conflict of interest will be required to have such conflicts managed in a way that is appropriate to their participation in the study. The study leadership in conjunction with the Sponsor has established policies and procedures for all study group members to disclose all conflicts of interest and will establish a mechanism for the management of all reported dualities of interest.

18 APPENDICES

18.1 Appendix I: List of NM21-1480 Formulation Excipients

- Water for injection

18.2 Appendix II: Liver Safety Monitoring and Assessment

Introduction

The purpose of this appendix is to provide guidance for the monitoring of drug-induced liver injury (DILI) during the course of the study. It should be noted that this section does not specify the end of study analyses of liver enzymes. The end of study liver enzymes analyses will be described in the SAP. Any patient enrolled in a study with active drug therapy and who reveals an increase of serum aminotransferases (AT) to $>3 \times$ ULN (to $>5 \times$ ULN in patients with liver metastases) or total bilirubin level (TBL) $>2 \times$ ULN should undergo detailed testing for liver enzymes (including at least ALP, ALT, AST and TBL). Testing should be repeated within 72 hours of notification of the test results. Patients should be asked if they have any symptoms.

Definition of Liver Abnormalities

Confirmed abnormalities will be characterized as moderate and severe where ULN is as shown in below table:

	ALT or AST		Total Bilirubin
Moderate	$>3 \times$ ULN (in patients without liver metastases), $>5 \times$ ULN (in patients with liver metastases)	or	$>2 \times$ ULN
Severe	$>3 \times$ ULN	and*	$>2 \times$ ULN

Abbreviations: ALT=alanine aminotransferase; AST=aspartate aminotransferase; ULN=upper limit of normal

*Samples taken simultaneously or within a maximum of 24 hours.

In addition, the patient should be considered to have severe hepatic abnormalities for any of the following:

- AST or ALT $>5-10 \times$ ULN for >2 weeks or AST or ALT $>10 \times$ ULN
- Total bilirubin $>5 \times$ ULN
- Concurrent AST or ALT $>3 \times$ ULN and total bilirubin $>2 \times$ ULN without initial finding of cholestasis (elevation of ALP)
- For patients with hepatic metastases: AST or ALT $>8 \times$ ULN or AST or ALT $>5 \times$ ULN for ≥ 14 daysThe Investigator may determine that abnormal liver function results, other than those described above, may qualify as moderate or severe abnormalities and require additional monitoring and follow-up

Follow-up Procedures

Confirmed moderate and severe abnormalities in hepatic functions should be thoroughly characterized by obtaining appropriate expert consultations, detailed pertinent history, physical examination and clinical laboratory tests. The study site personnel are to complete the eCRF. Patients with confirmed abnormal liver function tests (LFT) should be followed as described below:

Confirmed moderately or severely abnormal LFTs should be repeated 2 to 3 times weekly then weekly or less if abnormalities stabilize or the IP has been discontinued and the patient is asymptomatic.

Severe hepatic liver function abnormalities as defined above, in the absence of another etiology may be considered an important medical event and may be reported as an SAE. The Sponsor should be contacted and informed of all patients for whom severe hepatic liver function abnormalities possibly attributable to IP are observed.

To further assess abnormal hepatic laboratory findings, the Investigator is expected to:

- Obtain a more detailed history of symptoms and prior or concurrent diseases. Symptoms and new-onset diseases are to be recorded as “AEs” in the eCRF. Illnesses and conditions such as hypotensive events and decompensated cardiac disease that may lead to secondary liver abnormalities should be noted. Nonalcoholic steatohepatitis is seen in obese hyperlipoproteinemic and/or diabetic patients and may be associated with fluctuating AT levels. The Investigator should ensure that the medical history form captures any illness that predates study enrollment that may be relevant in assessing hepatic function;
- Obtain a history of concomitant drug use (including nonprescription medication, complementary and alternative medications), alcohol use, recreational drug use and special diets. Medications, including dose, are to be entered in the eCRF. Information on alcohol, other substance use and diet should be entered on the eCRF or an appropriate document;
- Obtain a history of exposure to environmental chemical agents;
- Based on the patient’s history, other testing may be appropriate including:
 - Acute viral hepatitis (A, B, C, D, E or other infectious agents)
 - Ultrasound or other imaging to assess biliary tract disease
 - Other clinical laboratory tests including international normalized ratio and direct bilirubin;
- Consider gastroenterology or hepatology consultations; and
- Submit results for any additional testing and possible etiology on the eCRF or an appropriate document.

Study Treatment Discontinuation

In the absence of an explanation for increased LFTs, such as viral hepatitis, pre-existing or acute liver disease, presence of liver metastases, or exposure to other agents associated with liver injury, the patient may be discontinued from study treatment. The Investigator may determine that it is not in the patient's best interest to continue study treatment. Discontinuation of study treatment should be considered if:

- AST or ALT $>5-10 \times$ ULN for >2 weeks or AST or ALT $>10 \times$ ULN
- Total bilirubin $>5 \times$ ULN
- Concurrent AST or ALT $>3 \times$ ULN and total bilirubin $>2 \times$ ULN without initial finding of cholestasis (elevation of ALP)
- For patients with hepatic metastases: AST or ALT $>8 \times$ ULN or AST or ALT $>5 \times$ ULN for ≥ 14 days

* Samples taken simultaneously or within a maximum of 24 hours.

In addition, if close monitoring for a patient with moderate or severe hepatic laboratory tests is not possible, study treatment should be discontinued.

Hy's Law Definition

1. Evidence that a drug can cause hepatocellular-type injury, generally shown by a higher rate than control of people with $3 \times$ AT elevations over the ULN ($2 \times$ elevations are too common in treated and untreated patients to be discriminating).
2. Cases of increased bilirubin (to at least $2 \times$ ULN) in people with concomitant AT elevation to at least $3 \times$ ULN (but it is almost invariably higher) and no evidence of intra- or extra-hepatic bilirubin obstruction (elevated ALP) or Gilbert's syndrome [Reference: Temple R. Hy's Law: Predicting Serious Hepatotoxicity. *Pharmacoepidemiol Drug Saf*.2006; 15(4):241-3].

FDA Guidance for Industry titled "DILI: Premarketing Clinical Evaluation" issued by the FDA on July 2009.

FDA Guidance for Industry:

1. The drug causes hepatocellular injury, generally shown by a higher incidence of 3-fold or greater elevations above the ULN of ALT or AST than the (nonhepatotoxic) control drug or placebo.
2. Among patients showing such AT elevations, often with AT levels much greater than $3 \times$ ULN, 1 or more also show elevation of serum TBL to $>2 \times$ ULN, without initial findings of cholestasis (elevated serum ALP).

3. No other reason can be found to explain the combination of increased AT and TBL, such as viral Hepatitis A, B or C; pre-existing or acute liver disease; or another drug capable of causing the observed injury.

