9.2.1.6 Adverse Event of Special Interest

An AESI must be reported as if it were an SAE ([Section 9.2.6](#)).

Elevations of ALT/AST that are >3 -fold above baseline are to be considered AESI and to be reported with SAE timelines. The details on how to handle such situations are provided in [Appendix VI](#), “Hepatitis”). In case of Grade 3+ hepatotoxicity, an initial ultrasound or image needs to be done to visualize the biliary tree and to rule out disease progression or occurrence of gall stones.

The following types of AESIs will be examined:

- AEs falling under the system order class (SOC) of hepatobiliary disorders (i.e., to cover any potential liver toxicity) Grade 3 or higher
- SOC of immune system disorders (i.e., to cover cytokine release syndrome and irAEs) Grade 3 or higher
- Any AE of CTCAE V5.0 Grade 3 or higher
- Any CTCAE V5.0 Grade 3 or 4 infusion reaction whether or not the event is a DLT or delayed DLT
- Any AE considered by the Investigator to represent a DLT or delayed DLT

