9.2.6 Reporting of SAEs

All SAEs must be reported according to ICH GCP or local regulations, applying the regulation with the stricter requirements. Investigators and other site personnel must inform Arriello of any SAE that occurs during the course of the study (from the time of informed consent until 70 days after the end of study visit), whether or not it is causally related to study drug or procedures, and within 24 hours of when they become aware of the event. An SAE with an onset greater than 70 days for the end of study visit will be recorded only for fatal SAEs, late-occurring irAEs, and those deemed by the Investigator to be treatment-related. The Investigator should make every effort to obtain follow-up information on the outcome until the event is considered resolved, chronic and/or stable.

If a non-serious AE becomes serious, this and other relevant follow-up information must also be provided to Arriello within 24 hours as described above. The start date of the SAE is not the AE start date, but the date when the AE becomes serious; analogously, the stop date is the date when any seriousness criterion is no longer applicable, not the date when the AE is resolved.

All SAEs will also be recorded in the eCRF. The Investigator is responsible for informing the Ethics Committee of the SAE as per local requirements. An SAE Report Form should be completed at the site and emailed within 24 hours of awareness of the event to the Central Receipt mailbox:

The SAE Report Form should be attached to the email; a notification email of the event describing it in the email text is not sufficient. There may be situations when an SAE has occurred and the Investigator has minimal information to include in the initial SAE Report Form. However, it is very important that the Investigator always makes an assessment of causality for every event prior to transmission of the SAE report form. Minimum criteria are identifiable participant (number), a suspect product (i.e., study drug or concomitant medication), an identifiable reporting source (Investigator/study site identification), and an event or outcome that can be identified as serious. Follow-up information on SAEs must also be reported by the Investigator within the same time frames.

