9.2.7.1 Potential Hy's Law and Hy's Law

Cases where a patient shows elevations in liver biochemistry may require further evaluation and occurrences of AST or ALT $\geq 3 \times$ ULN together with total bilirubin $\geq 2 \times$ ULN without evidence of intra- or extra-hepatic bilirubin obstruction (elevated at least ALP) or Gilbert's syndrome will need to be reported as SAEs. Please refer to [Appendix II, Section 18.2](#) for further instruction on cases of increases in liver biochemistry and evaluation of Hy's Law.

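### A potential Hy's Law case must be reported as an SAE under Protocol Section 9.2.7.1, but Appendix II, to which that section refers sites, says only that it may be

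*Protocol*

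**What the plan says.** Protocol Section 9.2.7.1 takes AST or ALT of at least 3 × ULN together with total bilirubin of at least 2 × ULN, with no evidence of biliary obstruction and no Gilbert's syndrome. It says that these occurrences "will need to be reported as SAEs". It then directs the reader to Appendix II (Section 18.2) "for further instruction on cases of increases in liver biochemistry and evaluation of Hy's Law". Section 9.2.6 sets the SAE clock: "within 24 hours of when they become aware of the event".

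Appendix II lists as severe, among other things, concurrent AST or ALT above 3 × ULN and total bilirubin above 2 × ULN "without initial finding of cholestasis (elevation of ALP"). Of the severe class as a whole it says that such abnormalities "in the absence of another etiology may be considered an important medical event and may be reported as an SAE". It adds: "The Sponsor should be contacted and informed of all patients for whom severe hepatic liver function abnormalities possibly attributable to IP are observed". No time limit is attached to that contact.

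Three other protocol provisions can start a 24-hour clock:

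- Section 9.2.1.6: "Elevations of ALT/AST that are >3 -fold above baseline are to be considered AESI", reported on SAE timelines.
- Section 9.2.1.6: any AE of Grade 3 or higher is an AESI, and so is any event that the Investigator considers a DLT or delayed DLT.
- Section 7.2.5.1: satisfying Hy's Law is a named DLT criterion, and every AE that meets DLT criteria is to be reported as an AESI within 24 hours.

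Section 10.6.6, however, says that AESIs need no expedited reporting to the Sponsor unless they meet SAE criteria.

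**The concern.** One laboratory picture carries two reporting duties, and the mandatory text sends the site to the permissive one. The background section describes dose-dependent hepatitis with an earlier antibody to the same target, and Section 5.3.2 reports a Grade 3 transaminase elevation in Part A, so this is a risk that the protocol itself names.

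Two things are at stake. The first is timing: a site that treats Appendix II as the operative instruction could make an untimed contact with the Sponsor instead of filing an SAE within 24 hours. The second is tabulation: SAP Section 3.6.2 summarises SAEs and treatment-emergent SAEs separately from AESIs. A case sent quickly as an AESI, but not classed as serious, would still be missing from the SAE tables.

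**Working it through.** The plan gives no figure to reproduce. The check has two parts.

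**1. The texts side by side** (multiples of ULN)

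| Place | AST/ALT | Bilirubin | ALP condition | Gilbert's excluded | Consequence |
|---|---|---|---|---|---|
| Protocol 9.2.7.1 | ≥3 | ≥2 | no obstruction | yes | SAE, mandatory |
| Appendix II, severe class | >3 | >2 | none in the table row; no cholestasis in the list | no | SAE optional |
| Appendix II, Hy's Law definition | ≥3 | ≥2 | no obstruction | yes | none stated |
| Protocol 7.2.5.1, DLT | >3 | >2 | ALP >2 or not available | no | AESI within 24 hours |
| SAP 3.6.3 | >3 | ≥2 | ALP <2, same visit | no | counted in a table |

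Apart from exact-threshold values, a non-cholestatic case meeting 9.2.7.1 also falls in the Appendix II severe class. The mandatory and optional wordings therefore apply to the same patients. The ALP condition in 7.2.5.1 runs opposite to that in 9.2.7.1.

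**2. Which cases reach no other 24-hour rule?**

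Inputs: baseline AST/ALT *b* of at most 2.0 × ULN (inclusion criterion 15); the 9.2.7.1 limits; the AESI limit of more than 3-fold above baseline; the 7.2.5.1 limits. Assumptions not in the documents: Grade 3 starts above 5 × ULN for AST/ALT (alternatively above 5 × baseline when baseline is abnormal) and above 3 × ULN for bilirubin. Bilirubin is set at 2.5 × ULN with ALP not raised. No other seriousness criterion, such as hospitalisation, is met.

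Leaving the DLT rule aside, an on-study value *a* (× ULN) meets 9.2.7.1 but no AESI limit when

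3 ≤ *a* ≤ min(3*b*, 5).

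| Baseline *b* | 3*b* | Band for *a* |
|---|---|---|
| below 1.0 | below 3.0 | empty |
| 1.0 | 3.0 | 3.0 only |
| 1.25 | 3.75 | 3.0–3.75 |
| 1.5 | 4.5 | 3.0–4.5 |
| 2.0 | 6.0 | 3.0–5.0 (3.0–6.0 if graded against baseline) |

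The 5 × ULN cap binds from *b* = 5/3 ≈ 1.67.

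Adding the DLT rule:

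- **No hepatic metastases, ALP wording taken literally.** A patient with normal ALP does not meet the Hy's Law criterion, so the bands stand.
- **No hepatic metastases, ALP wording taken to mean no ALP elevation.** The criterion catches everything above 3 × ULN with bilirubin above 2 × ULN. Only exact-threshold cases remain.
- **Hepatic metastases, with the separate limits (above 8 × ULN, or above 5 × ULN for at least 14 days) read as replacing the Hy's Law arm.** The bands stand up to 5 × ULN however ALP is read. Between 5 and 6 × ULN they stand only if the elevation is not sustained for 14 days.
- **Hepatic metastases, with those limits read as additional to the Hy's Law arm.** The result is the same as without metastases.

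Example: hepatic metastases, baseline ALT 2.0, on-study ALT 4.0, bilirubin 2.5 × ULN, normal ALP. The ratio is 4.0/2.0 = 2.0-fold, so the AESI limit is not met. Both values are below the assumed Grade 3 cuts, and 4.0 is below 5 and 8. Section 9.2.7.1 is met, and so is the Appendix II severe class. If the metastasis limits replace the Hy's Law arm, no other 24-hour rule applies.

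**The case against.** The best defence is that a site can comply with both texts. The severe class in Appendix II is broad: it includes isolated transaminase or bilirubin elevations, metastasis-specific limits, and a table row with no ALP condition. Discretion over that mixed class need not cancel a specific duty in the body of the protocol. The appendix presents itself as monitoring guidance, and its own Hy's Law definition has the same limits and the same Gilbert's exclusion as Section 9.2.7.1. That much stands. It would be wrong to infer that Appendix II sets different Hy's Law limits or that it repeals the mandatory rule. But the optional sentence carves nothing out, and Section 9.2.7.1 names Appendix II as the place for further instruction, so the conflict remains for the site to resolve.

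A reader might also infer that every eligible patient with baseline ALT between 1.0 and 2.0 × ULN has a window with no other fast-reporting rule. The documents do not support that, because the Hy's Law DLT criterion in Section 7.2.5.1 closes it under one reading of the ALP wording, except for exact-threshold values and for hepatic metastases if their limits replace that criterion. A judgement-based DLT clause (drug-related toxicity of any grade requiring removal from the study) could capture further cases. The DLT window is the first 28 days; after that, the route depends on the Investigator considering the event a delayed DLT.

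Nor would a missed case be invisible. SAP Section 3.6.3 counts potential Hy's Law cases from laboratory values whatever their SAE status, within its own limits, and Appendix II does ask that the Sponsor be told. Neither supplies a 24-hour clock.

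The AESI fallback is weaker than it looks, because Section 10.6.6 contradicts expedited AESI reporting and returns the site to the question of whether the event is an SAE.

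**Conclusion.** The inconsistency is real and rests on the text alone: SAE reporting of the same picture is mandatory in Section 9.2.7.1 and optional in Appendix II, with untimed Sponsor contact in the latter. The consequence is a possible omission from 24-hour SAE reporting and from the SAE and treatment-emergent SAE tables. It is not a loss of the case from the analysis.

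The group with no other 24-hour rule is narrow. Apart from exact-threshold values, it needs a baseline AST/ALT above ULN, an event below Grade 3, and either the literal ALP wording in Section 7.2.5.1 or hepatic metastases with their limits replacing the Hy's Law arm. The Grade 3 cuts are assumptions. Independently of them, Section 8.1.6 anticipates combined Grade 2 AST/ALT and bilirubin values that meet discontinuation parameters, so events of this kind below Grade 3 are foreseen.

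Few patients can be affected. Section 5.3.2 gives 26 exposed in Part A, and SAP Section 6 gives 5 in A-2, 5 in B1, 5 in B7 and 10 in B8: 26 + 5 + 5 + 5 + 10 = 51. How many had a raised baseline is not stated. The correction should be made because it is cheap and concerns safety reporting; no efficacy conclusion depends on it.

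**What to change.** - **Appendix II:** carve cases that meet the Hy's Law limits and exclusions shared by Section 9.2.7.1 and the appendix's own definition out of the optional sentence. State that they follow the mandatory SAE reporting of Sections 9.2.7.1 and 9.2.6. Keep discretion for the other severe categories.
- **Section 7.2.5.1:** reconcile the ALP wording with Section 9.2.7.1, and state whether the hepatic-metastases limits replace the Hy's Law arm or add to it.
- **Section 10.6.6:** reconcile its statement on AESI reporting with Sections 9.2.1.6 and 7.2.5.1.
- **Appendix II severe class and SAP Section 3.6.3:** align the boundary symbols and the Gilbert's exclusion with Section 9.2.7.1. Criterion 15 admits patients with Gilbert's syndrome and bilirubin up to 3.0 × ULN, who could otherwise be counted.
- **For data already collected:** apply the Section 9.2.7.1 limits to the laboratory data, and compare each case found with the SAE listing.

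The cost is a few sentences and symbols, one listing, and at most a few more SAE forms.
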